8.3.1 Analysis of Primary Efficacy Endpoint

The primary endpoint is the absolute change from baseline of Total Brody/CF-CT score at Week 72 using LDCT. The primary analysis will be based on an analysis of covariance (ANCOVA) model with the change from baseline of Total Brody/CF-CT score at Week 72 as dependent variable, treatment, sex (male versus female), and age (12-17 years vs. 18 years and older) as covariates. LDCT images will be scored by 2 central reader(s) blinded to treatment group and visit time point. The difference between the VX-661/ivacaftor group and the placebo group in mean change from baseline in Total Brody/CF-CT score at Week 72 will be estimated using the FAS.

The primary result obtained from the model will be the estimated treatment effect in each treatment group (with a 95% confidence interval), the estimated between-group difference in treatment effects, and a 95% confidence interval (CI) for the difference. For missing data, no imputation will be performed.

Summary statistics (n, mean, SD, SE, median, minimum, and maximum) will be presented by treatment group at each scheduled visit and for absolute change from baseline at each scheduled visit.

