Study Design This is a Phase 2, randomized, placebo-controlled, double-blind, parallel-group, multicenter study in subjects with CF who are homozygous for the *F508del-CFTR* mutation. This study is designed to evaluate the treatment effect of VX-661/ivacaftor on chest imaging endpoints over 72 weeks of treatment; LDCT [REDACTED] will be used for chest imaging.

All subjects will undergo LDCT imaging at specified time points. [REDACTED]

[REDACTED] The images will be evaluated using the Brody/CF-CT scoring system.

Safety during 72 weeks of treatment will also be evaluated.

This study includes a Screening Period, a 72-week Treatment Period, and a Safety Follow-up Visit. Following a 28-day Screening Period, approximately 40 subjects will be randomized (1:1) to 1 of the 2 treatment arms, active or placebo, on Day 1. The active treatment regimen will be comprised of a morning dose of a fixed-dose combination tablet of VX-661 100-mg/ivacaftor 150-mg and an evening dose of ivacaftor 150-mg to be taken approximately 12 hours after the morning dose. The placebo regimen will be visually-matched tablets to be taken on the same schedule as the active treatment.

The study will be double-blind. Interim analyses are described below in the “Statistical Analyses” section.

Assessments **Efficacy:** LDCT, [REDACTED]

[REDACTED]
Safety: AEs, clinical laboratory assessments (hematology, serum chemistry, vitamin levels, lipid panel, coagulation studies, and urinalysis), vital signs, physical examinations, pulse oximetry, and ECGs

Statistical Analyses Statistical analysis details will be provided in the Statistical Analysis Plan (SAP), which will be finalized before the clinical data lock for the study and treatment unblinding.

The primary endpoint is the change from baseline in Total Brody/CF-CT score at Week 72 using LDCT. The primary analysis will be based on an analysis of covariance (ANCOVA) model with the change from baseline in Total Brody/CF-CT score at Week 72 as dependent variable, and treatment, sex (male versus female), and age as covariates.

[REDACTED]
Safety data will be summarized descriptively by treatment group.

IDMC Reviews The independent data monitoring committee (IDMC) will conduct regular planned safety reviews of study data as outlined in the IDMC charter.

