Table 3-2 Study VX15-661-112: Treatment Period (Day 1 to Week 72), Early Termination of Treatment Visit, and Safety Follow-up Visit Assessments

Event/Assessment ^a	Day 1	Day 15 (± 3 days)	Week 4, Week 12, (± 1 week)	Week 24 (± 1 week)	Week 36, Week 48, Week 60 (± 1 week)	Week 72 (± 1 week)	Early Termination of Treatment Visit (Within 7 days After Last Dose of Study Drug)	Safety Follow-up Visit 4 weeks (± 7 days) After Last Dose of Study Drug ^b
Low-dose CT scan ^h	X					X		
Standard digital ECG ^m	X	X	X	X	X	X	X	X
Vital signs ⁿ	X	X	X	X	X	X	X	X
Pulse oximetry ⁿ	X	X	X	X	X	X	X	X

^h Low-dose CT scans [REDACTED] should be performed on the same day. If not possible for logistical reasons, Low-dose CT scans [REDACTED] should be performed within ± 4 days of the scheduled visit. Day 1 assessments must be completed before dosing. The Week 72 CT scan may be delayed for up to 60 days if the subject is recovering from a pulmonary exacerbation. The medical monitor should be notified about the extension. The scan should be done after the pulmonary exacerbation is resolved and at least 28 days after the antibiotic regimen for the treatment of pulmonary infection has been completed. If this antibiotic regimen is not completed by the end of the 60-day extension, the subject may complete the CT scan within the first 30 days of enrolling in Study VX14-661-110; or within 1 week of the end of the 60-day extension if they do not enroll in Study VX14-661-110. No extension is permitted for any other assessment.

All standard 12-lead ECGs will be performed before dosing and after the subject has been supine for at least 5 minutes. The predose ECGs collected at the Day 1 Visit will be performed in triplicate.

ⁿ Vital signs and pulse oximetry will be collected before dosing and after the subject has been at rest (seated or supine) for at least 5 minutes. In addition to the indicated visits, symptom-targeted vital signs will occur at any time during the study if triggered by AEs or if deemed necessary by the investigator.

Table 3-2 Study VX15-661-112: Treatment Period (Day 1 to Week 72), Early Termination of Treatment Visit, and Safety Follow-up Visit Assessments

Event/Assessment ^a	Day 1	Day 15 (± 3 days)	Week 4, Week 12, (± 1 week)	Week 24 (± 1 week)	Week 36, Week 48, Week 60 (± 1 week)	Week 72 (± 1 week)	Early Termination of Treatment Visit (Within 7 days After Last Dose of Study Drug)	Safety Follow-up Visit 4 weeks (± 7 days) After Last Dose of Study Drug ^b

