start of the study, the mean change in the Total Brody score was +2.2 points per year.¹⁹ Based on these longitudinal studies, it is estimated that the progression of disease observed in the proposed study population is a 3.3 point increase in the Total Brody Score at Week 72. There has been 1 study that has examined the impact of CFTR modulation on structural lung disease. In 10 subjects (ages 10 to 44 years) who carried the *CFTR-G551D* mutation, Sheikh et al reported a within-treatment annual improvement of 13.6 points in the Total Brody/CF-CT score after 1 year of ivacaftor treatment.²⁰

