12.3.3.1 Analysis of Primary Endpoint

The primary endpoint is the absolute change from baseline of Total Brody/CF-CT score at Week 72 using LDCT. The primary analysis will be based on an analysis of covariance

(ANCOVA) model with the change from baseline of Total Brody/CF-CT score at Week 72 as dependent variable, treatment, sex (male versus female), and age as covariates. LDCT images will be scored by 2 central reader(s) blinded to treatment group and visit time point, as described in [Section 11.5.1.3](#). The difference between the VX-661/ivacaftor group and the placebo group in mean change from baseline in Total Brody/CF-CT score at Week 72 will be estimated.

The primary result obtained from the model will be the estimated treatment effect in each treatment group (with a 95% confidence interval), the estimated between-group difference in treatment effects, and a 95% confidence interval (CI) for the difference. For missing data, no imputation will be performed.

Methodological details will be provided in the study SAP.

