13.2.3 Investigator Compliance

No modifications to the protocol will be made without the approval of both the investigator and Vertex. Changes that significantly affect the safety of the subjects, the scope of the investigation, or the scientific quality of the study (i.e., efficacy assessments) will require IRB/IEC notification before implementation, except where the modification is necessary to eliminate an apparent immediate hazard to subjects. Vertex will submit all protocol modifications to the required regulatory authorities.

When circumstances require an immediate departure from procedures set forth in the protocol, the investigator will contact Vertex to discuss the planned course of action. If possible, contact will be made before the implementation of any changes. Any departures from the protocol will be fully documented in the source documentation and in a protocol deviation log.

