8.2.2 Subject Demographics and Baseline Characteristics

[figure not shown]
Demographic and baseline characteristics data will be summarized based on the FAS.

Demographic data will include the following:

- Sex (female and male)
- Age
- Age group at screening (<18, and ≥18 years)
- Ethnicity (Hispanic or Latino, not Hispanic or Latino, and not collected per local regulations)
- Race (White, Black or African American, Asian, American Indian or Alaska Native, Native Hawaiian or Other Pacific Islander, and Other)

Baseline characteristics will include the following:

- Weight (kg)
- Height (cm)

Disease characteristics will include the following:

- Percent predicted FEV₁ at baseline
- Sweat Chloride at screening
- Use of dornase alfa
- Use of inhaled antibiotic
- Use of bronchodilator
- Use of inhaled bronchodilator
- Use of inhaled hypertonic saline
- Use of inhaled corticosteroids
- Colonization of *Pseudomonas aeruginosa* (Positive, Negative)

- Brody/CF-CT total score at baseline

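### The primary ANCOVA on change in Total Brody/CF-CT score omits the baseline score, so a chance baseline imbalance between two arms of 20 can carry into the estimate

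*SAP*

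**What the plan says.** The outcome of the primary ANCOVA is the change in total CT score from Day 1 to Week 72. Three places give its model terms, and none includes the baseline score:

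- Protocol Synopsis, Statistical Analyses: "dependent variable, and treatment, sex (male versus female), and age as covariates".
- Protocol 12.3.3.1: "treatment, sex (male versus female), and age as covariates".
- SAP 8.3.1: "treatment, sex (male versus female), and age (12-17 years vs. 18 years and older) as covariates".

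The baseline score is available for every subject scanned on schedule. Footnote h of Protocol Table 3-2 says of the imaging visit: "Day 1 assessments must be completed before dosing". SAP 8.2.2 lists "Brody/CF-CT total score at baseline" among the disease characteristics to be summarized. In the visible text its only other use is in computing the change.

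The SAP splits age into two groups where the protocol says only age. The protocol leaves such details to the SAP, and that difference is not part of this point.

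**The concern.** Subtracting baseline is not the same as adjusting for it. An analysis of change with no baseline term assumes that a subject who starts 10 points higher will on average also end 10 points higher. If the real relationship is flatter, the arm that happens to start with higher scores will tend to show the smaller increase whatever the treatment does. Part of the chance imbalance then appears as treatment effect. A slope below 1 is plausible because the score is semiquantitative and assigned by readers, and reading error in the baseline score flattens the slope. The documents do not give the slope.

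The estimated difference and its 95% CI are the primary result, and Protocol 12.1 and SAP 6.2 say the sample size has no power basis. The trial's contribution is therefore that one estimate. The baseline table would reveal an imbalance, but no visible text says how it would be handled, and adding the covariate after seeing it would be a post hoc choice.

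**Working it through.** The plan has no power calculation to reproduce. The check is how far an imbalance moves the estimate, and what adjustment does to the CI.

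**Inputs from the documents.** 20 subjects per arm, allocated 1:1 (Protocol 10.3 and 12.1); model terms as quoted; expected untreated progression of a "3.3 point increase in the Total Brody Score at Week 72" (Protocol 8.2.2).

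**Assumptions, none given in the documents.** Baseline SD (SD0) of 12 points, range 8 to 16; correlation rho between baseline and Week 72; ratio k of the Week 72 SD to the baseline SD; simple randomization; all 40 subjects analysed; sex and age group unrelated to baseline score.

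**Size of a chance imbalance.** The SE of the difference in baseline means is SD0 x sqrt(2/20) = 0.316 SD0, or 3.79 points at SD0 = 12. The probability of an imbalance beyond one SE in either direction is 0.317. Beyond 0.5 SD it is 0.11.

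**Shift in the estimate.** The true slope is b = rho x k. A baseline difference d shifts the change-score estimate by (b - 1) x d. For d of one SE and SD0 = 12, the shift in points is (b - 1) x 3.79:

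| k | rho 0.5 | rho 0.7 | rho 0.8 | rho 0.9 |
|---|---|---|---|---|
| 1.0 | -1.90 | -1.14 | -0.76 | -0.38 |
| 1.1 | -1.71 | -0.87 | -0.46 | -0.04 |
| 1.2 | -1.52 | -0.61 | -0.15 | +0.30 |

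At rho 0.9 the shift vanishes at k = 1/0.9 = 1.11 and changes sign beyond it.

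**Shift against the SE of the estimate.** That SE is SD0 x sqrt((2/20)(1 + k^2 - 2 x rho x k)). At k = 1 it is 2.94, 2.40 and 1.70 points for rho 0.7, 0.8 and 0.9. The ratios are 1.14/2.94 = 0.39, 0.76/2.40 = 0.32 and 0.38/1.70 = 0.22, and they do not depend on the assumed SD.

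**Shift against the 3.3-point progression.** At k = 1 and SD0 = 12 the same shifts are 35%, 23% and 11% of 3.3 points. Over SD0 from 8 to 16 they run from 0.25 points (rho 0.9) to 1.52 points (rho 0.7), or 8% to 46%.

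**Simulation of the two models** (6,000 trials per cell, 20 per arm, no treatment effect, t quantiles on 36 and 35 df). Mean 95% CI half-width in points, without and then with baseline:

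| k | rho 0.5 | rho 0.7 | rho 0.8 | rho 0.9 | rho 0.95 |
|---|---|---|---|---|---|
| 1.0 | 7.84, 6.89 | 6.09, 5.70 | 4.95, 4.77 | 3.52, 3.48 | 2.48, 2.49 |
| 1.1 | 8.29, 7.61 | 6.43, 6.27 | 5.27, 5.26 | 3.76, 3.82 | 2.72, 2.73 |
| 1.2 | 8.75, 8.29 | 6.86, 6.85 | 5.68, 5.75 | 4.15, 4.17 | 3.13, 2.98 |

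The largest gain is about 12% and the largest loss about 1.5%. At k = 1 the estimate regressed on the imbalance has slope -0.51, -0.30, -0.21, -0.09 and -0.05 across the five correlations, close to rho - 1. With baseline in the model the slope is about 0. Over all randomizations both models are essentially unbiased, with 94% to 96% coverage.

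**Coverage given an imbalance.** A second simulation (20,000 trials per correlation, k = 1) looked at trials with a baseline difference of 0.4 to 0.6 SD. The planned interval covers 91%, 93% and 95.6% of the time at rho 0.5, 0.7 and 0.9. The adjusted interval covers 94.3%, 94.1% and 95.7%.

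**The case against.** The strongest reply is that this is not an error. Protocol and SAP agree, the model is pre-specified, and under randomization its estimate is unbiased with nominal coverage. The random effect of baseline imbalance is already inside the SE of a change-score difference. A one-SE imbalance moves the estimate by well under half its SE, and at rho 0.9 conditional coverage hardly suffers. All of this stands, and it limits the point to conditional bias and precision.

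The figures in points rest on an assumed SD, correlation and SD ratio, and with k above about 1.1 the shift can be nil or reversed. That also stands. In addition, 3.3 points is untreated progression rather than a treatment effect. Against the 13.6-point annual improvement that Protocol 8.2.2 cites for ivacaftor in 10 subjects with another mutation, 0.38 to 1.14 points is about 3% to 8%. If age group or sex explains part of the baseline score, the terms already in the model remove some of the imbalance.

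Parts of SAP 6.3 and 8.3 are redacted, so a stratification factor or a supportive adjusted analysis may exist. The sentence defining the primary model is fully visible, however. The trial is labelled exploratory and has no decision threshold attached to the CI.

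None of this favours leaving the covariate out. Uncertainty about the slope is a reason to estimate it rather than fix it at 1, and estimating it costs almost nothing.

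**Conclusion.** The concern holds. The baseline score is absent from the primary model in all three places, and adding it removes the dependence of the estimate on baseline imbalance. The effect is moderate at most: 0.22 to 0.39 of an SE for a one-SE imbalance at rho 0.9 to 0.7 with equal SDs, larger at lower correlation, and close to nil where the slope is near 1. The SE-unit figures depend on the assumed correlation and SD ratio, and those in points also on the assumed SD. The main benefit is protection against imbalance. The precision gain is modest and can be nil. This should be fixed, with medium confidence in how much it will matter in this trial.

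**What to change.** Before database lock and treatment unblinding, add baseline Total Brody/CF-CT score as a continuous covariate to the primary ANCOVA in SAP 8.3.1. Keep the model with treatment, sex and age as a supportive analysis. Either align Protocol 12.3.3.1 and the Synopsis, or record the added covariate in the SAP as a change from the protocol-planned analysis.

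The cost is one line in the SAP, one degree of freedom, no new data, and at most about 1.5% in CI width in the settings tried. Real baseline scores are already supplied for blinded programming (Protocol 10.12.1). If the protocol is amended as well, Section 13.2.3 applies: "No modifications to the protocol will be made without the approval of both the investigator and Vertex". It also requires IRB/IEC notification if the change is judged to significantly affect scientific quality.

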9.1 Inclusion Criteria

Subjects who meet all of the following inclusion criteria will be eligible for this study:

1. Subject (or his or her legally appointed and authorized representative) will sign and date an informed consent form (ICF), and where appropriate, assent form
2. Willing and able to comply with scheduled visits, treatment plan, study restrictions, laboratory tests, contraceptive guidelines, and other study procedures
3. Subjects (males and females), will be 12 years of age or older on the date of informed consent or, where appropriate, date of assent
4. Homozygous for the *F508del-CFTR* mutation, genotype to be confirmed with testing performed at the Screening Visit. If the *CFTR* screening genotype result is not received before randomization, a previous *CFTR* genotype laboratory report may be used to establish eligibility. *Note: Subjects who have been randomized and whose screening genotype results do not confirm study eligibility must be discontinued from the study as described in Section 9.5. CFTR genotyping may be waived if the subject has a documented result from a previous Vertex study.*
5. Confirmed diagnosis of CF³¹ defined as a sweat chloride value ≥ 60 mmol/L by quantitative pilocarpine iontophoresis. A sweat chloride test must be performed at the Screening Visit if an eligible sweat chloride value is not available in the subject's medical records and the Screening Visit value is needed to establish eligibility. For subjects using sweat chloride values documented in their medical records to establish eligibility, the sweat chloride test at the Screening Visit is optional.
6. $ppFEV_1 \geq 70\%$ of predicted normal for age, sex, and height (equations of Wang et al. or Hankinson et al.)^{36,37} during screening. Spirometry measurements must meet American Thoracic Society/European Respiratory Society criteria¹⁷ for acceptability and repeatability.
7. Stable CF disease as judged by the investigator
8. Willing to remain on a stable CF medication regimen through the end of the treatment period (up to 72 weeks) and, if applicable, the ETT visit and the Safety Follow-up Visit

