10.3 Method of Assigning Subjects to Treatment Groups

Approximately 40 subjects who meet the eligibility criteria will be randomized (1:1) to 1 of 2 treatment arms.

An interactive web response system (IWRS) will be used to assign subjects to treatment. The randomization code will be produced by Vertex Biostatistics or a qualified randomization vendor. The Vertex study biostatistician will review and approve the production of the final

randomization list, which will be reviewed and approved by a designated unblinded biostatistician who is not a member of the Study Execution Team.

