6.3 Randomization

Approximately 40 subjects who meet the eligibility criteria will be randomized (1:1) to 1 of 2 treatment arms.

An interactive web response system (IWRS) will be used to assign subjects to treatment. The IWRS will use a list of randomization codes generated by a designated vendor [REDACTED].

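### Does the SAP change the primary model by splitting age at 18 where the protocol lists only age?

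*SAP*

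**What the plan says.** The protocol synopsis and Protocol 12.3.3.1 give the model terms as "treatment, sex (male versus female), and age as covariates". Levels are stated for sex and none for age. Neither place says whether age enters in years or in groups. Section 12.3.3.1 then closes with "Methodological details will be provided in the study SAP".

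SAP 8.3.1 keeps the same model and fixes the age term: "age (12-17 years vs. 18 years and older) as covariates". SAP 8.2.2 lists age and, as a separate item, "Age group at screening (<18, and ≥18 years").

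Protocol 9.1 sets a lower age limit only: a subject "will be 12 years of age or older on the date of informed consent". On allocation, Protocol 10.3 says "Approximately 40 subjects who meet the eligibility criteria will be randomized (1:1) to 1 of 2 treatment arms" and names no stratification factor. SAP 6.3 says "The IWRS will use a list of randomization codes generated by a designated vendor", and the text directly after that is redacted.

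**The concern.** Because the protocol gives levels for sex and none for age, many readers would take age to mean years. The SAP then inserts a cut at 18 with no visible explanation, so the two documents could be read as specifying different primary models.

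Cutting a continuous covariate usually discards information. With no upper age limit, all adults share one covariate value. If the 72-week change in Total Brody/CF-CT score varies gradually with age through adulthood, the split absorbs less residual variance and the confidence interval is wider than it need be. The only efficacy output named in these sections is an estimate with a 95% interval from about 40 subjects, so precision matters.

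SAP 8.3.1 also does not say on what date the 12-17 class is fixed. Seventy-two weeks is 504 days, or about 1.4 years, so a subject aged roughly 16.6 to under 18 on Day 1 turns 18 before the final scan. SAP Appendix D does let the spirometry reference standard change at a birthday.

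**Working it through.** **No stated figure to reproduce.** The documents give no SD, target difference or power for this endpoint. Protocol 12.1 gives 40 subjects at 1:1, so 40/2 = 20 per arm, which agrees with the text.

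**Step 1: is there a contradiction?** The protocol names the covariate and leaves the detail to the SAP. The SAP names the same covariate and supplies its form. Only one document states a form, so nothing conflicts. SAP section 3 requires the SAP to be final before database lock, so the form is fixed in advance.

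**Step 2: bias.** Age is a pre-treatment variable and allocation is randomised. With complete data, either form targets the same difference. In simulated trials (n = 40, treatment + sex + age term), the mean error was at most 0.01 SD for both forms, and 95% interval coverage was 0.94 to 0.96.

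**Step 3: precision if the age effect is linear.** Let rho be the correlation of age with change and c the squared correlation of age with the under-18 indicator. Both models spend 1 df on age, so

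SE(split)/SE(years) = sqrt[(1 − rho²c)/(1 − rho²)].

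For uniform ages with a fraction p below 18, c = 3p(1 − p). The documents give neither rho nor the age distribution, so the following are assumptions.

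| Assumed ages | Share under 18 | c | rho 0.3 | rho 0.5 |
|---|---|---|---|---|
| Uniform 12-30 | 6/18 = 33% | 0.67 | +1.6% | +5.4% |
| Uniform 12-45 | 6/33 = 18% | 0.45 | +2.7% | +8.8% |
| 12 + gamma(2, scale 6) | 26% | 0.35 | +3.2% | +10.3% |
| 12 + gamma(1.5, scale 8) | 32% | 0.37 | +3.1% | +10.0% |

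Example, first row, rho 0.3: sqrt[(1 − 0.09 × 0.67)/(1 − 0.09)] = sqrt(0.940/0.910) = 1.016. At rho 0 the ratio is 1. A separate simulation with other assumed age distributions gave interval-width increases of 2 to 3% at rho 0.3, 7 to 10% at 0.5 and 20 to 25% at 0.7.

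**Step 4: precision if the age effect is not linear.** If change steps at 18, the ratio inverts to sqrt[(1 − rho²)/(1 − rho²c)]. At rho 0.5 this is 1/1.054 = 0.949 (c = 0.67) to 1/1.103 = 0.907 (c = 0.35), so the split is 5 to 9% more precise. Simulation (20,000 trials per setting, same four age distributions) gives the intermediate shapes, split relative to years:

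| True shape | rho 0.3 | rho 0.5 |
|---|---|---|
| Logarithmic | +1.3 to +2.3% | +4 to +7% |
| Plateau at 30 | +0.8 to +1.7% | +3 to +5% |
| Plateau at 22 | +0.1 to −1.5% | +0.5 to −4.5% |
| Step at 18 | −1.6 to −3.0% | −5 to −9% |

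Even with a linear effect (gamma(2, 6) ages, rho 0.3), the split gave the narrower interval in about 27% of simulated trials.

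**Step 5: keeping both age terms.** If the second term adds nothing, the 95% interval is about 1.5% wider on average at n = 40 (35 instead of 36 df). That is a mean, not a ceiling: the 95th percentile was about 6%.

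**Step 6: reference date.** SAP 8.2.2 defines under 18 and 18 or over at screening. Since entry starts at 12, those are the two classes in 8.3.1. An ANCOVA covariate is a baseline quantity, so an analyst would use that variable.

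**The case for a change.** The best case for a change is that unbiased on average does not mean the same answer in this trial. In simulations the two models' estimates differed with a between-trial SD of 0.07 to 0.10 outcome SD at rho 0.3 (23 to 32% of the standard error) and 0.10 to 0.14 at rho 0.5 (36 to 51%). Age in years needs no new data and no extra df, and it matches the more natural reading of the protocol.

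The first part stands: the form can visibly move the estimate. That is an argument for fixing one form before unblinding, which SAP 8.3.1 does. It does not show that years is the better form. The protocol's natural-history progression figure (Protocol 8.2.2) comes from children with a mean starting age of 11 and says nothing about a trend through adulthood.

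A second point concerns bias. Missing scans are not imputed. If missing Week 72 scans depended on age in opposite directions in the two arms, the split would leave a bias of about 0.03 to 0.10 SD (rho 0.3 to 0.5) that a correct linear term removes. That scenario was built to be extreme, and nothing in the documents points to it.

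The lack of a visible reason carries little weight. The redaction in SAP 6.3 falls where a stratification factor could be described. The SAP contents list puts 8.3.1 on page 12 and 8.4 on page 19, yet only a few short paragraphs of that span can be read. Neither a missing reason nor a missing sensitivity model can be inferred.

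**Conclusion.** The wording differs, but the SAP specifies what the protocol left open. The choice between the split and years is a fair trade-off: equal df, no bias under randomisation with complete data, and a standard error that moves by about −9% to +10% for correlations up to 0.5, depending on the shape of the age effect. A larger loss, with intervals 20 to 25% wider, needs a linear correlation of 0.7. All of these figures rest on assumed age distributions and curves.

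Replacing a prespecified term with a linear one would exchange one untested shape for another, in an exploratory study with no power claim. The missing cross-reference to the age group at screening is a gap that analysts would fill in the obvious way. No change to the plan follows.
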